5.4.1. Criteria for Study Termination

The Investigator, competent authority, or Sponsor may terminate the study for reasonable cause. Conditions that warrant termination of the study include, but are not limited to, the following:

- Discovery of an unexpected, serious, or unacceptable risk to subjects enrolled in the study
- Decision on the part of the Sponsor to suspend or discontinue testing, evaluation, or development of the study drug
- Failure of the Investigator to comply with the approved protocol, pertinent guidelines, and/or regulations
- Submission of knowingly false information from the Investigator to the Sponsor and/or regulatory authorities

6. STUDY DRUG

Study drug is defined as any investigational drug product(s), marketed product(s), or placebo, intended to be administered to a subject according to the protocol.

6.1. Study Drug Administered

The study drug composition and doses to be administered in this study are presented in Table 6.

Ravulizumab IV Ravulizumab SC rHuPH20 Ravulizumab Study Drug Name: SC/rHuPH20 Dosage Ravulizumab IV is Ravulizumab SC rHuPH20 is Ravulizumab Formulation: formulated at pH 7.0 is formulated at supplied as SC/rHuPH20 is and each vial pH 7.4 and each ENHANZE® drug formulated per the contains 300 mg of vial contains product (EDP) is individual ravulizumab in 1100 mg of supplied in vials as components of the ravulizumab in 10 mM sodium a sterile, singledrug product. phosphate, 150 mM 50 mM sodium dose, injectable liquid at sodium chloride, phosphate, 25 0.02% polysorbate mM arginine, 5% approximately sucrose, and 110 kU/mL. The 80. 0.05% solution has a pH of 6.5 and contains Each vial contains polysorbate 80. 10 mg/mL. 130 mM sodium chloride, 10 mM Each vial contains 100 mg/mL. L-Histidine/ hydrochloride as a buffer. 10 mM L-Methionine. and 0.2% w/w polysorbate 80. The solution is filled to 0.5 mL in a 2-mL glass vial. ravulizumab SC Unit Dose 400 mg 400 mg NA 500 mg/rHuPH20 Strength(s)/ Dosage Level(s): 10,000 units ravulizumab SC 1000 mg/rHuPH20 20,000 units ravulizumab SC 2000 mg/rHuPH20 40,000 units SC SC IV Route of SC Administration

 Table 6:
 Dose Reference Chart for Study ALXN1210-HV-105

Study Drug Name:	Ravulizumab IV	Ravulizumab SC	rHuPH20	Ravulizumab SC/rHuPH20
Dosing Instructions:	A single dose of ravulizumab IV will be administered via IV infusion and 80 mL of ravulizumab IV will be administered at a maximum infusion rate of 333mL/hr, for a minimum infusion duration of approximately 15 minutes. Use of an in-line filter for infusion is required.	A single dose of ravulizumab SC will be administered via SC infusion administered by a syringe pump. The total volume to be administered will be 4 mL at an infusion rate of 0.5 mL/min.	NA	Ravulizumab will be co-mixed with EDP in empty, sterile 20-mL glass vials. A single dose of ravulizumab SC/rHuPH20 will be administered via SC infusion, administered via an infusion pump. The total volume to be administered for the combination cohorts will be 5.23 mL in Cohort 2, 10.46 mL in Cohort 3, and 20.91 mL in Cohort 4 at an infusion rate of 2 mL/min
Packaging and Labeling Additional instructions are provided in the pharmacy manual.	Ravulizumab IV drug product will be provided in a single-use, USP/Ph Eur Type 1 clear and colorless glass vial, stoppered with a gray butyl rubber stopper, and sealed with aluminum seal with a polypropylene flip-off cap.	Ravulizumab SC drug product will be provided in a single-use, USP/Ph Eur Type 1 clear and colorless glass vial, stoppered with a gray butyl rubber stopper, and sealed with aluminum seal with a polypropylene flip-off cap.	rHuPH20 for coadministration will be provided as single-use, USP/Ph Eur Type I clear and colorless glass vial.	Individual components of ravulizumab SC/ rHuPH20 drug product will be packaged and labeled according to their respective manufacturers.
Manufacturer	Alexion	Alexion	Halozyme	Alexion/Halozyme

Abbreviations: IV = intravenous; NA = not applicable; SC = subcutaneous. Source: rHuPH20 Investigator's Brochure (2018), pharmacy manual

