6.2. Preparation/Handling/Storage/Accountability

- 1. The Investigator or designee must confirm appropriate temperature conditions have been maintained during transit for all study drug received and that any discrepancies are reported and resolved before use of the study drug.
- 2. Only subjects enrolled in the study may receive study drug and only authorized site staff may supply or administer study drug. All study drugs must be stored in a secure, environmentally controlled, and monitored (manually or automated) area in accordance with the labeled storage conditions with access limited to the Investigator and authorized site staff.

- 3. Preparation of ravulizumab IV, ravulizumab SC, and the ravulizumab SC/rHuPH20 drug products must be performed in accordance with local standards by qualified pharmacy personnel at the investigative site.
- 4. The handling and preparation of materials used to prepare and administer the study drug must be carried out using aseptic techniques for sterile products. For each subject, doses will be prepared as required per the dose cohort.
- 5. The entire dosing apparatus (ie, syringe and infusion tubing) should be weighed before and after infusion and the weights recorded for the purpose of recoding the exact dose administered.
- Recombinant human hyaluronidase PH20 will be supplied as ENHANZE drug product (EDP; 1 mg/mL [0.5 mg of active ingredient per vial; approximately 110,000 units/mg]) in 2-mL single use glass vials.
- 7. The volume of drug product to be prepared will be based on the cohort to which a subject is assigned. For Cohort 1, ravulizumab will be administered undiluted via SC infusion administered by a syringe pump. For Cohorts 2 through 4, ravulizumab will be co-mixed with EDP in empty, sterile glass vials. A single dose of ravulizumab SC/rHuPH20 will be administered via SC infusion administered by a syringe pump. For Cohort 5, the IV admixture will consist of ravulizumab diluted in a 1:1 ratio with 0.9% sodium chloride, Ph Eur, or BP. Do not flush the IV infusion line. The rate at which study drug will be administered in Cohorts 1 through 4 will be provided in the pharmacy manual.
- 8. The Investigator or qualified designee is responsible for study drug accountability, reconciliation, and record maintenance (ie, receipt, reconciliation, and final disposition records).

Additional instructions are provided in the pharmacy manual.

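### Do the Table 6 infusion volumes for Cohorts 2–4, about 2.7% above the sum of the two named components, need correcting?

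*Protocol*

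**What the plan says.** Protocol Section 6.1, Table 6, gives ravulizumab SC at 100 mg/mL in vials of 1100 mg, and EDP at about 110 kU/mL in vials filled to 0.5 mL. Section 6.2, item 6, agrees on the EDP strength: "EDP; 1 mg/mL [0.5 mg of active ingredient per vial; approximately 110,000 units/mg".

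For the combination cohorts Table 6 says "Ravulizumab will be co-mixed with EDP in empty, sterile 20-mL glass vials" and gives total volumes of "5.23 mL in Cohort 2, 10.46 mL in Cohort 3, and 20.91 mL in Cohort 4". Section 6.2, item 7, repeats the mixing step: "For Cohorts 2 through 4, ravulizumab will be co-mixed with EDP in empty, sterile glass vials". The planned doses are 500 mg/10,000 units, 1000 mg/20,000 units and 2000 mg/40,000 units (Section 4.1, Table 4).

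For the SC control, which Section 6.2 says is given undiluted, Table 6 states: "The total volume to be administered will be 4 mL at an infusion rate of 0.5 mL/min". For the IV control, Section 6.2 names the diluent: "For Cohort 5, the IV admixture will consist of ravulizumab diluted in a 1:1 ratio with 0.9% sodium chloride".

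Table 6 ends with "Source: rHuPH20 Investigator's Brochure (2018), pharmacy manual", and Section 6.2 closes with "Additional instructions are provided in the pharmacy manual". SAP Section 4.13.2 divides AUC by the actual dose, taken from the weight of drug given.

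**The concern.** The printed strengths and doses reproduce the two control volumes exactly but not the three combination volumes. This is the first time the combination is given to humans, and a reader working from the protocol alone cannot tell what fills the last 2.7% of each infusion.

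There is also a possible route into the primary pharmacokinetic result. If the weighed dose is turned into milligrams with the wrong mix concentration, the error falls only on the combination cohorts. It would then carry straight into absolute bioavailability (against Cohort 5) and relative bioavailability (against Cohort 1).

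**Working it through.** **Inputs.** Ravulizumab SC 100 mg/mL, EDP 110,000 units/mL, vial contents and stated volumes from Sections 6.1 and 6.2; doses from Table 4.

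**Control cohorts first.**
- Cohort 1: 400/100 = 4 mL, as printed.
- Cohort 5: 400/10 = 40 mL, doubled by the 1:1 dilution to 80 mL, as printed.

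**Combination cohorts, two components at full strength.** Volume = mg/100 + units/110,000.

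| Cohort | Ravulizumab (mL) | EDP (mL) | Sum (mL) | Stated (mL) | Excess (mL) | Excess as % of sum |
|---|---|---|---|---|---|---|
| 2 | 5.00 | 0.091 | 5.091 | 5.23 | 0.139 | 2.73 |
| 3 | 10.00 | 0.182 | 10.182 | 10.46 | 0.278 | 2.73 |
| 4 | 20.00 | 0.364 | 20.364 | 20.91 | 0.546 | 2.68 |

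**Explanations that do not close the gap.**
- Looseness in the EDP potency. The potency needed is units/(stated mL − mg/100) = 43,478, 43,478 and 43,956 units/mL, about 40% of the listed strength.
- A weaker ravulizumab solution. It would have to be about 97.3 mg/mL, which Cohort 1 contradicts.
- A fixed line or dead-volume allowance. The excess grows with dose, 1 : 2.00 : 3.93.

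**What the pattern suggests.** Stated dose over stated volume is 500/5.23 = 95.60, 1000/10.46 = 95.60 and 2000/20.91 = 95.65 mg/mL. A near-constant concentration points to one recipe scaled by dose. Table 6's own vial sizes supply a candidate: one ravulizumab vial (1100 mg in 11 mL) plus 0.5 mL, the EDP fill volume, making 11.5 mL at 1100/11.5 = 95.65 mg/mL. Volume is then mg × 11.5/1100:
- Cohort 2: 5.227 mL (stated 5.23)
- Cohort 3: 10.455 mL (stated 10.46, which is 2 × 5.23)
- Cohort 4: 20.909 mL (stated 20.91)

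The stated doses call for 20 units per mg, hence 22,000 units per 1100 mg. In 0.5 mL that is 44,000 units/mL, matching the 43.5–44.0 kU/mL solved for above. EDP pre-diluted to that strength would give 10,000, 20,000 and 40,000 units with 500, 1000 and 2000 mg.

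**Largest effect on bioavailability.** The two-component mix would be 500/5.091 = 98.21 mg/mL. Using it where the true figure is 95.60, or the reverse, gives a factor of 98.21/95.60 = 1.027, or 0.027 on the log scale. For 12 against 6 subjects, the 95% half-width is t(0.975, 16) × √ln(1 + CV²) × √(1/12 + 1/6):
- CV 20%: 2.120 × 0.198 × 0.5 = 0.210
- CV 30%: 2.120 × 0.294 × 0.5 = 0.311

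The documents give no between-subject CV; 20–30% is an assumption.

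**The case for a change.** The strongest case for a change has four parts.

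1. Section 6.2 names a diluent for Cohort 5 and none for Cohorts 2–4, so a reader will take the list of components as complete, and on that reading the printed figures conflict. This is fair comment on the text. But the same item calls only Cohort 1 undiluted. The protocol says neither that EDP is used neat nor that nothing else is added. The conflict needs that extra premise.

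2. The 11 mL plus 0.5 mL recipe is a guess, and with undiluted EDP it would carry 2.5 times the stated units. That is true: it works only with a pre-dilution that the protocol does not mention. The recipe proves nothing about what was prepared. It shows only that the printed doses and volumes can hold together.

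3. Section 4.1 allows reduced doses in Cohorts 3 and 4 without an amendment, and no volume is printed for them. The protocol alone would give two slightly different answers, at 95.6 or 98.2 mg/mL. The gap in the text stands. Preparation, however, is done by qualified pharmacy staff and detailed in the manual, which Table 6 cites as a source.

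4. The weight-to-milligram conversion needs the mix concentration, and an error there would not cancel in the ratios. The direction of the argument is right, but the proposed cure is incomplete. Grams convert to milligrams through density as well as mg/mL, and the documents give no density for any cohort, including Cohort 1, where mg/mL is known. The missing conversion rule is a general gap that the Table 6 volumes did not create.

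**Conclusion.** The subtraction is correct, and the protocol does not say what makes up the 0.14, 0.28 and 0.55 mL. What it shows is preparation detail kept outside the protocol. It does not show a wrong dose, a wrong volume or a biased ratio. The printed doses and volumes fit a single fixed mix at about 95.65 mg/mL with one unlisted step. Section 4.3's 2,000 U/mL equals the units over the ravulizumab volume alone (10,000/5). Over the stated total volume it is about 1,912 U/mL, so that figure too has to be read together with the make-up of the mix.

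Writing the recipe into Table 6 would alter no analysis. If the conversion uses the actual mix concentration, the effect on both bioavailability ratios is zero. The worst case is 0.027 on the log scale, roughly a tenth of the assumed half-width.

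This rests on the inferred recipe and on a pharmacy manual that is not among the documents. Sections 4.3, 6.1 and 6.2 have to be reconciled with that manual at preparation, and I take no view on which volume, strength or unit dose is right. The plan needs no change on this point.

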6.2. Preparation/Handling/Storage/Accountability

- 1. The Investigator or designee must confirm appropriate temperature conditions have been maintained during transit for all study drug received and that any discrepancies are reported and resolved before use of the study drug.
- 2. Only subjects enrolled in the study may receive study drug and only authorized site staff may supply or administer study drug. All study drugs must be stored in a secure, environmentally controlled, and monitored (manually or automated) area in accordance with the labeled storage conditions with access limited to the Investigator and authorized site staff.

- 3. Preparation of ravulizumab IV, ravulizumab SC, and the ravulizumab SC/rHuPH20 drug products must be performed in accordance with local standards by qualified pharmacy personnel at the investigative site.
- 4. The handling and preparation of materials used to prepare and administer the study drug must be carried out using aseptic techniques for sterile products. For each subject, doses will be prepared as required per the dose cohort.
- 5. The entire dosing apparatus (ie, syringe and infusion tubing) should be weighed before and after infusion and the weights recorded for the purpose of recoding the exact dose administered.
- Recombinant human hyaluronidase PH20 will be supplied as ENHANZE drug product (EDP; 1 mg/mL [0.5 mg of active ingredient per vial; approximately 110,000 units/mg]) in 2-mL single use glass vials.
- 7. The volume of drug product to be prepared will be based on the cohort to which a subject is assigned. For Cohort 1, ravulizumab will be administered undiluted via SC infusion administered by a syringe pump. For Cohorts 2 through 4, ravulizumab will be co-mixed with EDP in empty, sterile glass vials. A single dose of ravulizumab SC/rHuPH20 will be administered via SC infusion administered by a syringe pump. For Cohort 5, the IV admixture will consist of ravulizumab diluted in a 1:1 ratio with 0.9% sodium chloride, Ph Eur, or BP. Do not flush the IV infusion line. The rate at which study drug will be administered in Cohorts 1 through 4 will be provided in the pharmacy manual.
- 8. The Investigator or qualified designee is responsible for study drug accountability, reconciliation, and record maintenance (ie, receipt, reconciliation, and final disposition records).

Additional instructions are provided in the pharmacy manual.

6.3. Measures to Minimize Bias: Randomization and Blinding

This is an open-label study. Eligible subjects who meet all inclusion and no exclusion criteria will be assigned unique numbers for enrollment and randomization. Randomization will only be used when cohorts are being enrolled in parallel.

- In order to minimize selection bias in treatment assignment, subjects will be randomly or sequentially assigned subject numbers, depending upon cohort, up to 7 days prior to dosing on Day 1, in the same order as they have become eligible.
- Sentinel dosing will be employed in Cohorts 1 through 4 (ie, 2 subjects in a cohort with 12 subjects and 1 subject in a cohort with 6 subjects will be dosed prior to dosing the remaining subjects within the cohort). Remaining subjects within the cohort will be dosed at least 24 hours following dosing of the sentinel subjects.
- At the Sponsor's discretion, and after consultation with the SRC, up to 16 additional subjects may be enrolled as replacement subjects if any subject discontinues prior to Day 50 for reasons other than drug-related AE.
- Study numbers will not be reallocated once assigned.

6.4. Study Drug Compliance

Subjects will be administered study drug in a controlled setting under the supervision of the Investigator, thereby ensuring compliance with study drug administration. Study center personnel will ensure that all subjects are adequately informed about the specific study drug dosing regimen required for compliance with the study protocol.

6.5. Concomitant Therapy

Subjects must abstain from taking prescription or nonprescription drugs (including vitamins and dietary or herbal supplements) within 14 days before the start of study drug until completion of the follow-up visit, unless, in the opinion of the Investigator and Sponsor, the medication will not interfere with the study.

Multivitamins, paracetamol (acetaminophen) (at doses of ≤ 2 g/day), and topical skin products without significant systemic absorption are permitted for use during the study at the Investigator's discretion. Topical skin products should not be administered at the site of study drug injection from 24 hours prior until 24 hours following study drug administration. Subjects are also permitted to receive a booster vaccine, if required.

Other concomitant medication may be considered on a case-by-case basis by the Investigator in consultation with the medical monitor if required. Concomitant procedures are not allowed unless medically indicated.

6.6. Contraception Guidance

Female subjects who are documented as being of non-childbearing potential as defined in Section 10.4 (Appendix 4) are exempt from contraception requirements.

Female subjects of childbearing potential, if heterosexually active, must use highly effective or acceptable contraception as defined below. Antibiotic prophylaxis is required during this study, which can compromise the efficacy of hormonal contraception. Therefore, subjects using hormonal contraception must also use barrier contraception (eg, condom or diaphragm with spermicide) for the duration of antibiotic prophylaxis.

Highly effective contraceptive methods for females are as follows:

- Combined (estrogen- and progestogen-containing) hormonal contraception associated with inhibition of ovulation as follows:
 - Oral
 - Intravaginal
 - Transdermal
- Progestogen-only hormonal contraception associated with inhibition of ovulation as follows:
 - Oral
 - Injectable
 - Implantable

- Intrauterine device
- Intrauterine hormone-releasing system
- Bilateral tubal occlusion

Male subjects, if heterosexually active and with a female spouse or partner of childbearing potential or a pregnant or breastfeeding spouse or partner, must agree to use barrier contraception (male condom). Barrier contraception is required even with documented medical assessment of surgical success of a vasectomy. Female spouses or partners of male subjects who are of childbearing potential must use highly effective contraception as defined above, or acceptable contraception as defined below. Male subjects must not donate sperm and female subjects must not donate ova.

Acceptable contraceptive methods are as follows:

• Simultaneous use of male condom and, for the female partner, occlusive cap (diaphragm or cervical/vault caps) with intravaginally applied spermicide

Contraception must start during screening and continue after the end of the systemic exposure of the study drug as specified below:

- Cohorts 1 and 5 contraception must continue for at least 6 months after last dose. Male subjects must not donate sperm and female subjects must not donate ova until at least 6 months after last dose.
- Cohorts 2, 3, and 4 contraception must continue for at least 8 months after last dose. Male subjects must not donate sperm and female subjects must not donate ova until at least 8 months after last dose.

6.7. Dose Modification

Decisions to continue, modify (explore the dose cohort further), or escalate dosing will be made by the Investigator and/or SRC as described in Table 7. The SRC may also make recommendations regarding safety issues, study conduct, or study suspension. The SRC is composed of the Sponsor's medical monitor, biostatistician, pharmacovigilance representative, clinical pharmacologist, and the Investigator. The membership roster, schedule of meetings, data required for each safety review, and requirements for documenting meeting discussions and outcome will be outlined in the SRC charter.

The SRC will review all available safety and tolerability data from a given cohort for at least the first 168 hours after study drug administration in order to determine whether to escalate the ravulizumab SC/rHuPH20 dose and initiate the next cohort. Data through 168 hours must be available for at least 11 of the 12 subjects. Dose escalation or modification will occur based on the recommendation of the SRC to dose escalate and only applies to Cohort 3 and Cohort 4.

Dosing Decision	Responsib le Party	Data to be Reviewed	Documentation/Communication Methods
Continuation from the sentinel subject to the remaining subjects in Cohort 1	Investigato r	A minimum of 24 hours post- dose safety and tolerability data from the sentinel subject.	The Investigator will document the decision in an email to the Sponsor. The email does not require the Sponsor's response, unless there is disagreement with the Investigator's decision.
Continuation from the sentinel subjects to the remaining subjects in Cohort 2	Investigato r	A minimum of 24 hours post- dose safety and tolerability data from the sentinel subjects.	The Investigator will document the decision in an email to the Sponsor. The email does not require the Sponsor's response, unless there is disagreement with the Investigator's decision.
Escalation to Cohort 3	SRC	A minimum of 168 hours post- dose safety and tolerability data from at least 11 subjects (all of whom have received treatment) from the previous cohort that was on the next lowest dose level (and hence, next lowest exposure) of ravulizumab SC/rHuPH20.	The SRC will document the decision on the escalation/progression approval form.
Continuation from the sentinel subjects to the remaining subjects in Cohort 3	Investigato r	A minimum of 24 hours post- dose safety and tolerability data from the sentinel subjects.	The Investigator will document the decision in an email to the Sponsor. The email does not require the Sponsor's response, unless there is disagreement with the Investigator's decision.
Escalation to Cohort 4	SRC	A minimum of 168 hours post- dose safety and tolerability data from at least 11 subjects (all of whom have received treatment) from the previous cohort that was on the next lowest dose level (and hence, next lowest exposure) of ravulizumab SC/rHuPH20.	The SRC will document the decision on the escalation/progression approval form.
Continuation from the sentinel subjects to the remaining subjects in Cohort 4	Investigato r	A minimum of 24 hours post- dose safety and tolerability data from the sentinel subjects.	The Investigator will document the decision in an email to the Sponsor. The email does not require the Sponsor's response, unless there is disagreement with the Investigator's decision.

Table 7:	Study ALXN1210-HV-105 Dose Continuation/Escalation Decision Pathway

Abbreviations: SC = subcutaneous; SRC = Safety Review Committee.

